#### 6.6 Dose Modifications for Hyponatremia

Grade	Action	Dose Modification
Grade 1 130 mmol/L to $<LLN$	
 
Be certain sodium level is corrected for hyperglycemia (serum glucose <math>> 150</math> mmol/L).
 
	Maintain dose.

THIS PROTOCOL IS FOR RESEARCH PURPOSES ONLY, SEE PAGE 1 FOR USAGE POLICY

	
 
• Rule out other causes of low sodium (e.g., cardiac, hepatic, adrenal, renal and thyroid diseases, SIADH, Fanconi Syndrome, hyperglycemia, diuretic use).
 
• Consider salt supplementation one – two times per day.
 
	
129 – 126 mmol/L (asymptomatic)	
 
• Be certain sodium level is corrected for hyperglycemia (serum glucose > 150 mmol/L).
 
• Rule out other causes of low sodium (e.g., cardiac, hepatic, adrenal, renal and thyroid diseases, SIADH, Fanconi Syndrome, hyperglycemia, diuretic use).
 
• Initiate salt supplementation two-three times per day.
 
	Hold selinexor until Grade ≤ 1, resume at same dose level.
≤ 125 mmol/L or any symptomatic Grade 3	
 
• Correct sodium as per institutional guidelines
 
• Initiate salt supplementation two-three times per day.
 
	Hold selinexor until Grade ≤ 1, resume at lower dose level.

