## 2.4 Adult Studies

In phase 1 clinical trials in adults with advanced solid or hematological malignancies (NCT01607905, NCT01607892, and NCT01896505). Selinexor was administered to over 240 patients. The dose limiting toxicities (DLTs) on the initial solid tumor trial were anorexia/nausea/dehydration and fatigue at 40  $\text{mg}/\text{m}^2$  (10 times per 4-week cycle; Days 1, 3, 5 of weeks 1 & 3 and Days 1 & 3 of weeks 2 & 4). The MTD and recommended phase 2 dose (RP2D) for 10 times per cycle dosing is 30  $\text{mg}/\text{m}^2$ . Reduced intensity dosing at twice weekly (8 times per cycle, Days 1 & 3 of each week) has shown improved tolerability, with an approximately 50% reduction in the observed rate of adverse effects. One of 6 patients at a dose of 35  $\text{mg}/\text{m}^2$  on the twice weekly schedule experienced a DLT of Grade 3 nausea, vomiting and fatigue; this patient also experienced concomitant *C. difficile* infection. Dose escalation cleared the 40  $\text{mg}/\text{m}^2$ , 50  $\text{mg}/\text{m}^2$  and 65  $\text{mg}/\text{m}^2$  levels without DLT, but there were 2 DLTs at 85  $\text{mg}/\text{m}^2$ : hyponatremia and reversible cerebellar syndrome. Based on these results, MTD and RP2D of selinexor twice weekly is determined to be 65  $\text{mg}/\text{m}^2$ .

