**Amendment #4:**

Week	Day	Agent: Selinexor
1	1	X
2	8	X
3	15	X
4	22	X

With Amendment #4, patients will receive selinexor once weekly, on Days 1, 8, 15, and 22 of a 28-day cycle. The drug will be administered in tablet form with food. Patients may continue for a maximum of 24 cycles. Refer to [Section 7.3](#) for recommended supportive care guidelines.

Drug doses should be adjusted based on the BSA calculated from height and weight measured within 7 days prior to the beginning of each cycle (See [Appendix VI](#)). If a dose is vomited within 30 minutes of administration and there is visible evidence of the tablet, the dose should be repeated. If the tablet is not visible, or the dose is vomited later than 30 minutes after administration, the dose should not be repeated. The patient/caregiver should make a note of the vomited dose and whether there is visible evidence of the tablet on the pill diary and proceed with the next dose at the next scheduled time of administration.

Selinexor is supplied by Karyopharm Therapeutics. **Do not use commercial supply.**

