GENERAL DISORDERS AND	Other, specify (asthenia)

THIS PROTOCOL IS FOR RESEARCH PURPOSES ONLY, SEE PAGE 1 FOR USAGE POLICY

ADMINISTRATION SITE CONDITIONS	
GENERAL DISORDERS AND ADMINISTRATION SITE CONDITIONS	Fatigue
GENERAL DISORDERS AND ADMINISTRATION SITE CONDITIONS	Peripheral edema
INFECTIONS AND INFESTATIONS	Other, specify
INFECTIONS AND INFESTATIONS	Sepsis
INVESTIGATIONS	Creatinine increased
INVESTIGATIONS	Weight loss
METABOLISM AND NUTRITION DISORDERS	Anorexia
METABOLISM AND NUTRITION DISORDERS	Dehydration
METABOLISM AND NUTRITION DISORDERS	Hyperglycemia
METABOLISM AND NUTRITION DISORDERS	Hypokalemia
METABOLISM AND NUTRITION DISORDERS	Hypomagnesemia
METABOLISM AND NUTRITION DISORDERS	Hyponatremia
NERVOUS SYSTEM DISORDERS	Dizziness
NERVOUS SYSTEM DISORDERS	Dysgeusia
NERVOUS SYSTEM DISORDERS	Headache
NERVOUS SYSTEM DISORDERS	Insomnia
PSYCHIATRIC DISORDERS	Confusion
RESPIRATORY, THORACIS AND MEDIASTINAL DISORDERS	Dyspnea

As referenced in the CTEP Adverse Events Reporting Requirements, an AE that resolves and then recurs during a subsequent cycle does not require CTEP-AERS reporting unless (1) the Grade increases; or (2) hospitalization is associated with the recurring AE.

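### Section 6.6 prints the glucose trigger for correcting sodium as > 150 mmol/L (about 2,700 mg/dL), which is unworkable and probably a unit error for 150 mg/dL

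*Combined protocol and SAP*

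**What the plan says.** Section 6.6 of the protocol sorts low sodium into three rows.

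- **Grade 1 (130 mmol/L to below the lower limit of normal).** The glucose instruction is "Be certain sodium level is corrected for hyperglycemia (serum glucose > 150 mmol/L". The dose instruction is "Maintain dose". Salt supplements are to be considered once or twice a day.
- **"129 – 126 mmol/L (asymptomatic").** The glucose instruction and its threshold are the same. The dose instruction is "Hold selinexor until Grade ≤ 1, resume at same dose level". Salt supplements are to be started two or three times a day.
- **125 mmol/L or below, or symptomatic Grade 3.** This row has no glucose trigger. It leaves correction of sodium to institutional practice, and selinexor is held and then resumed at a lower level.

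The first two rows also carry a second, threshold-free instruction: "Rule out other causes of low sodium (e.g., cardiac, hepatic, adrenal, renal and thyroid diseases, SIADH, Fanconi Syndrome, hyperglycemia, diuretic use". No other section of the public text gives a glucose threshold or restates this one in another unit.

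Under the current schedule in Section 5.1 (Amendment #4), "patients will receive selinexor once weekly, on Days 1, 8, 15, and 22 of a 28-day cycle".

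**The concern.** The sodium values in this table are properly in mmol/L, and the glucose value carries the same unit. As a glucose concentration, 150 mmol/L is clinically implausible, whereas 150 mg/dL is an ordinary level at which to begin correcting sodium. A slip of unit is the likely explanation.

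The number sits at an operative boundary. On one side the dose is maintained; on the other it is held and salt supplementation is stepped up. A patient with raised glucose can have a measured sodium just below 130 and a corrected sodium at or above it. With a trigger that can never be met, that patient stays in the hold row.

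Raised glucose is plausible in this trial. Section 7.3.1 recommends dexamethasone or prednisone around selinexor dosing as appetite support, and Section 7.3.6 describes glucocorticoid premedication continued for 48 hours after dosing. The Section 13.1 list of Grade 1 and 2 events exempt from expedited reporting includes "Hyperglycemia" as well as hyponatremia. None of this gives a rate for either event or for the two together.

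**Working it through.** The plan contains no calculation to reproduce here; the only stated figure is the threshold itself.

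**Inputs**

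- Printed trigger: glucose > 150 mmol/L (Section 6.6, first two rows).
- Row boundary: 130 mmol/L sodium; affected band 126 to 129 mmol/L, asymptomatic (Section 6.6).
- Doses per cycle: 4 (Section 5.1, Amendment #4).
- Molar mass of glucose: 180.156 g/mol, a physical constant not in the documents, so 1 mmol/L = 18.0156 mg/dL.
- Assumption, not in the documents: measured sodium falls by k = 1.6 to 2.4 mmol/L for each 100 mg/dL of glucose above 100 mg/dL.

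**Step 1: convert the unit.** 150 mmol/L × 18.0156 = 2,702 mg/dL. In the other direction, 150 mg/dL ÷ 18.0156 = 8.3 mmol/L.

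**Step 2: is the printed trigger workable?** The correction is k × (glucose − 100)/100. At 2,702 mg/dL it is 1.6 × 26.02 = 41.6 to 2.4 × 26.02 = 62.5 mmol/L. A trigger at which the correction starts at roughly 42 to 62 mmol/L cannot serve a table whose middle row spans 126 to 129.

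**Step 3: what glucose would move a patient out of the hold row?** Setting corrected sodium to 130 gives glucose = 100 + 100 × (130 − measured sodium)/k.

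| Measured sodium (mmol/L) | Glucose needed, k = 2.4 to 1.6 (mg/dL) | Same, in mmol/L |
|---|---|---|
| 129 | 142 to 163 | 7.9 to 9.0 |
| 128 | 183 to 225 | 10.2 to 12.5 |
| 127 | 225 to 288 | 12.5 to 16.0 |
| 126 | 267 to 350 | 14.8 to 19.4 |

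Every entry is far below 150 mmol/L, so the literal trigger would not operate for any of these patients.

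**Step 4: how much does the presumed trigger do?** At 150 mg/dL the correction is 0.8 to 1.2 mmol/L. A measured 129 becomes 129.8 to 130.2, which is on the boundary. At 200 mg/dL the correction is 1.6 to 2.4 mmol/L:

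- 129 becomes 130.6 to 131.4, in the maintain row.
- 128 becomes 129.6 to 130.4, depending on k.
- 127 becomes 128.6 to 129.4 and 126 becomes 127.6 to 128.4; both stay in the hold row.

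**Step 5: what is the consequence in doses?** The Grade 1 row already maintains the dose and the lowest row has no glucose trigger, so the printed error changes the action only in the middle row. If the resulting hold spans a dosing day, the loss is 1 of 4 doses in that cycle; otherwise no dose is lost.

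**The case against.** The strongest reply is that no clinician would apply 2,700 mg/dL literally. The instruction is to make certain of the correction, and the bracket only glosses it. The next bullet in the same cells requires hyperglycemia to be excluded as a cause, with no threshold. An unneeded hold therefore needs several things together: asymptomatic sodium of 126 to 129, glucose high enough to reclassify the patient, literal use of the printed number, and the second bullet passed over. A lost dose needs, in addition, a hold that spans a weekly dosing day. This largely stands and is why the point is minor. It does not make the printed number right: the second bullet supplies no threshold, so it does not replace the faulty one.

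It can also be said that the reclassification figures rest on an outside correction factor. That is true of Steps 2 to 4 in their detail. The unit conversion does not depend on it.

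A reader might infer that the error leads to dose reductions. It does not: the affected row resumes at the same level, and the row that lowers the dose carries no glucose trigger.

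A reader might also infer that it distorts the determination of the MTD. Section 5.5.1 does count a Grade 2 or higher non-hematological toxicity lasting at least 7 days as dose-limiting if it is significant or intolerable enough to require two omitted doses in a cycle. Section 5.5 also requires at least possible attribution to selinexor. A low sodium explained by glucose would have to meet all of that, and the hyperglycemia check would have to be missed. The route exists, so an effect on DLT counts cannot be excluded outright, but it is remote.

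**Conclusion.** The threshold is wrong as written, and the severity is minor. The unit conversion is certain and the printed value is unworkable. That 150 mg/dL was meant is an inference from plausibility; the documents do not state it.

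The realistic effect is an unneeded temporary hold, with at most one of four doses lost for each dosing day spanned, in an asymptomatic patient measured at 126 to 129 mmol/L whose corrected sodium would be Grade 1. Which patients would be reclassified depends on the assumed factor of 1.6 to 2.4 mmol/L per 100 mg/dL. How often this would happen cannot be estimated, because the protocol gives no rate of hyperglycemia. No sample size or error-rate calculation uses this number.

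A reader might conclude that the table also needs a new rule for assigning patients to rows by corrected sodium. The text does not support adding one: the table already tells sites to correct sodium, and a rule confined to the first two rows would treat the lowest row differently without a stated reason.

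**What to change.** After the sponsor confirms the intended value, change the unit in both cells of Section 6.6 to > 150 mg/dL (8.3 mmol/L). No new allocation rule is needed, and neither the row for 125 mmol/L or below nor the schedule in Section 8.1 needs to change. Section 2.4 reports that the two dose-limiting events in adults at 85 mg/m² were "hyponatremia and reversible cerebellar syndrome"; the correction leaves the lowest sodium row as strict as it is now.

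The cost is two table cells in the next amendment, with no extra test, visit or blood draw.

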## 6.7 Dose Modifications for Hepatic Adverse Events

6.7.1 If a patient experiences Grade ≥ 2 total bilirubin increase, treatment will be held. If toxicity resolves to Grade ≤ 1 within 7 days, the drug may be resumed at the same dose. Grade ≥ 2 total bilirubin increase that persists ≥ 7 days will be considered dose-limiting and require dose modification per [Section 6.2](#).

6.7.2 If a patient experiences Grade ≥ 3 ALT or AST, treatment will be held. If toxicity resolves to Grade ≤ 1 within 7 days, the drug may be resumed at the same dose. Grade ≥ 3 ALT or AST that persists ≥ 7 days will be considered dose-limiting and require dose modification per [Section 6.2](#).

## 7.0 SUPPORTIVE CARE AND OTHER CONCOMITANT THERAPY

### 7.1 Concurrent Anticancer Therapy

Concurrent cancer therapy, including chemotherapy, radiation therapy, immunotherapy, or biologic therapy may NOT be administered to patients receiving study drug. If these treatments are administered the patient will be removed from protocol therapy.

### 7.2 Investigational Agents

No other investigational agents may be given while the patient is on protocol therapy.

### 7.3 Supportive Care

Clinical observations in over 400 adult patients treated with selinexor have indicated that the dose limiting toxicities (DLTs) are primarily related to anorexia, fatigue, nausea, vomiting, and diarrhea and with poor caloric and fluid intake leading to dehydration and weight loss. Significant fatigue and somnolence have also been noted in pediatric studies. Prophylactic use of 5-HT3 anti-nausea / antiemetic therapy is strongly recommended, and

THIS PROTOCOL IS FOR RESEARCH PURPOSES ONLY, SEE PAGE 1 FOR USAGE POLICY

further supportive care with acid suppression (proton pump inhibitors and/or H2-blockers), glucocorticoids, and other standard treatments should be administered as per institutional guidelines for symptomatic patients, keeping in mind that nausea and vomiting related to selinexor is often delayed.

Below are recommendations based on the experience of the adult clinical trials and the DFCI pediatric leukemia trial but do not represent required treatment approaches should the toxicities occur. The administration of supportive care is as per institutional guidelines and the treating provider.

### 7.3.1 Anorexia/Weight loss

Selinexor treatment can lead to anorexia, decreased food intake with subsequent weight loss. Participants should be weighed at least weekly during study-required outpatient visits during cycle 1 and biweekly during cycles 2 and 3. If the patient is admitted for dehydration or malnutrition, more frequent weight assessment is recommended. It is strongly recommended that patients receive ongoing nutritional assessment and dietary support consultation. Administration of high caloric beverages (e.g., Pediasure®) should be considered for all patients. The use of supplemental tube feeding is acceptable.

Patients who experience decreased food/liquid/caloric intake secondary to anorexia should have a patient log of food and drink with monitoring by the treatment team. Fresh juices, simple carbohydrates, as well as ginger-containing foods and beverages can improve appetite.

Supportive care should be escalated for  $\geq$  Grade 1 anorexia or weight loss. **Guidelines for standard appetite stimulants are provided in the table below. The use of low dose olanzapine has been the most helpful in the control of nausea and anorexia in adult studies using selinexor.** Olanzapine for appetite stimulation and the treatment of chemotherapy induces nausea and vomiting, has not been thoroughly studied in children, and may have overlapping side effects with selinexor, including sedation and dizziness. For pediatrics, the suggested starting dose of olanzapine is approximately 0.06 mg to 0.1 mg/kg for patients < 10 years, 1.25 mg PO qPM for patients 10 – 12 years old or 2.5 mg PO qPM for patients > 12 years old. Patients who exhibit no response after 4 weeks, defined as no weight gain or further loss, may increase by 1.25 mg/day weekly to maximum 2.5 mg/day for children < 10 years, 5 mg/day for children ages 10 – 12, and 10 mg/day for children older than 12 years; use caution escalating olanzapine doses in patients younger than 10 years. Olanzapine may be given in combination with a corticosteroid. Either dexamethasone < 0.25 mg/kg daily (max dose: 10 mg) or prednisone < 0.5 mg/kg daily (max dose: 20 mg) is recommended on the days of, and 1 day after, selinexor dosing.

Additional recommended agents are megestrol acetate (10 mg/kg/dose by mouth once daily; max dose: 800 mg/day) or cyproheptadine at a dose of 0.25 mg/kg/day orally in two divided doses and as second line. Dronabinol has also shown some activity in both nausea/emesis and anorexia in patients treated with selinexor.

Anorexia or Weight Loss		
Grade	Action	Dose Modification
Grade 1	
 
• Rule out other causes of anorexia.
 
	Maintain dose.

THIS PROTOCOL IS FOR RESEARCH PURPOSES ONLY, SEE PAGE 1 FOR USAGE POLICY

	
 
Assess dietary options (e.g., try a variety of other foods).
 
Add high-calorie supplements (e.g., Pediasure®).
 
Consider adding olanzapine: the suggested starting dose of olanzapine is 0.06 mg to 0.1 mg/kg for patients < 10 years, 1.25 mg PO qPM for patients 10 – 12 years old or 2.5 mg PO qPM for patients > 12 years old.
 
	
Grade ≥ 2	
 
Rule out other causes of anorexia.
 
Assess dietary options (e.g., try a variety of other foods).
 
Add high-calorie supplements (e.g., Pediasure®).
 
Consider adding olanzapine: the suggested starting dose of olanzapine is 0.06 mg to 0.1 mg/kg for patients < 10 years, 1.25 mg PO qPM for patients 10 – 12 years old or 2.5 mg PO qPM for patients > 12 years old. Patients who exhibit no response after 4 weeks may increase by 1.25 mg/day weekly to maximum 5 mg/day for children ages 10 – 12 and 10 mg/day for children older than 12 years; use caution escalating olanzapine doses in patients younger than 10 years.
 
Consider addition of < 0.25 mg/kg (max 10 mg/dose) dexamethasone or equivalent with each dose of selinexor +/- the day after selinexor.
 
Consider megestrol acetate (10 mg/kg/dose by mouth once daily; max 800 mg/day) or cyproheptadine at a dose of 0.25 mg/kg/day orally in two divided doses
 
Consider anabolic steroids such as oxandrolone, or dronabinol or other cannabinoid, mainly for patients who can't tolerate steroids or at high risk to progress.
 
	See Section 6.3

### 7.3.2 Nausea and Emesis

**Prophylactic treatment of nausea and emesis is strongly recommended during Cycles 1 and 2 and will be required for any dose level with the suffix “A” (e.g. 1A, 2A).** See [https://childrensoncologygroup.org/downloads/COG\\_SC\\_CINV\\_Guidelines\\_Document\\_Feb\\_2018.pdf](https://childrensoncologygroup.org/downloads/COG_SC_CINV_Guidelines_Document_Feb_2018.pdf) for COG-endorsed antiemetic guidelines. If not instituted prophylactically, antiemetic therapy should begin once there is any indication of nausea as outlined in [Section 6.4](#).

#### 7.3.2.1 *Acute Emesis (occurring within 24 hours of administration of selinexor)*

Acute emesis has not frequently occurred with selinexor, but has been reported. Selinexor associated nausea/emesis generally responds to D2-antagonists (e.g. hydroxyzine), 5-HT3 antagonists (e.g. ondansetron), or combinations of agents. 5-HT3 receptor antagonists all appear equally effective at preventing nausea/emesis at standard doses. The efficacy of 5-HT3 receptor antagonists is significantly improved when combined with glucocorticoids. As QTc prolongation is the main side effect, magnesium and potassium should be corrected prior to use.

THIS PROTOCOL IS FOR RESEARCH PURPOSES ONLY, SEE PAGE 1 FOR USAGE POLICY

Neurokinin-1 receptor antagonists (e.g., aprepitant) should be considered once uncontrolled emesis persists despite the use of the above recommended standard treatments. Neurokinin-1 receptor antagonists can be given with combination of dexamethasone and 5-HT3 receptor antagonists.

Additional treatment: Metoclopramide hydrochloride has been effective when given prior to meals (up to 4 times a day) in adult patients. Dronabinol has shown some activity in both nausea/emesis and anorexia in patients treated with selinexor. Lorazepam can be added to the combination treatment of 5-HT3 receptor antagonists and dexamethasone, e.g., at night, but has been less effective in selinexor associated nausea and emesis.

#### 7.3.2.2 *Delayed Emesis (occurring greater than 24 hours after administration of selinexor)*

Selinexor is infrequently associated with delayed, resistant emesis. Many of the regimens associated with delayed emesis are classified as high-emetic risk, and professional guidelines recommend the use of an NK1 receptor antagonist (either NK-1 blockers e.g., aprepitant on days 1 to 3 or fosaprepitant on day 1 only), plus a glucocorticoid on days 1 to 4, along with a 5-HT3 receptor antagonist (particularly second generation agents) on day 1. This regimen is effective against both acute and delayed emesis.

Conventional antiemetics are more successful at preventing emesis than in preventing nausea, particularly delayed nausea. As previously noted, in adult studies, olanzapine given once daily (typically given at night to mitigate sedative effects) was effective in both antiemetic and nausea control. It may also be useful for management of breakthrough emesis, and to improve food intake in patients with anorexia. Olanzapine for the treatment of chemotherapy induced nausea and vomiting, has not been thoroughly studied in children, and may have overlapping side effects with selinexor, including sedation and dizziness. Guidelines for olanzapine use in pediatrics can be found in [Section 7.3.1](#).

The following additional agents have been administered in the adult population: lorazepam, alprazolam, dopaminergic D2-antagonists (eg, prochlorperazine, thiethylperazine, haloperidol), or substituting high-dose intravenous metoclopramide for the 5-HT3 antagonist.

#### 7.3.3 Diarrhea

Refer to [Section 6.5](#).

#### 7.3.4 Dysgeusia

Suggested foods that can reduce metallic taste include sour foods that are rich in citric acid like orange juice or vitamin C drops. Avoid sweets. Oral hygiene should be optimized.

#### 7.3.5 Ophthalmic Toxicities

Some episodes of blurred vision in adult clinical studies of selinexor have responded to IV hydration and have been attributed to dehydration. Therefore, IV hydration to correct any clinical deficits should be considered for blurred vision.

THIS PROTOCOL IS FOR RESEARCH PURPOSES ONLY, SEE PAGE 1 FOR USAGE POLICY

For blurred vision that does not improve with hydration within 24 hours, or any other ophthalmic toxicity grade 2 or higher, assessment by an ophthalmologist is strongly recommended. As of June 19, 2020, 2 of 42 patients enrolled on ADV1414 have reported a serious adverse event of grade 4 vision loss, both of whom had tumors affecting the optic chiasm in the setting of tumor progression. Blurred vision is a known side effect of selinexor and described as generally mild, not accompanied by objective changes on ophthalmologic exam and nearly always resolves. However, a contribution of selinexor to blurred vision cannot be ruled out.

